### 4.3 DISCONTINUATION/WITHDRAWAL OF STUDY SUBJECTS

#### 4.3.1 CRITERIA FOR DISCONTINUATION OF INVESTIGATIONAL PRODUCT

Subjects who manifest a Grade 4 toxicity attributable to the study treatment will be discontinued from the study treatment. Subjects will not receive further study treatment/EP but will be encouraged to continue follow-up safety assessment through study discharge and not discontinue from the study.

If a subject manifests a Grade 3 toxicity attributable to study treatment/EP, the medical monitor and PI will discuss whether further treatment should be continued for that subject.

### 4.3.2 CRITERIA FOR WITHDRAWAL FROM THE STUDY

All subjects who begin treatment should be encouraged to complete all phases of the study, including those who discontinue treatment. A subject may voluntarily withdraw from study participation at any time. A subject may be withdrawn at any time at the discretion of the Investigator for any maternal obstetrical or medical complications after consultation with the medical monitor.

Subjects who become ineligible to continue on study based on no longer meeting exclusion criteria should be discontinued from study treatment, managed per routine standard of care and should continue on study without further biopsy.

Subjects who are withdrawn from study participation after starting treatment will not be replaced. Reasons for study withdrawal will be recorded in the electronic case report form (eCRF) and the subject's source document.

Should a subject fail to attend the clinic for a required study visit, the site should attempt to contact the subject and reschedule the missed visit as soon as possible. The site should also counsel the subject on the importance of maintaining the assigned visit schedule for follow-up and treatment of VIN, and ascertain whether or not the subject wishes to and/or should continue in the study based on previous noncompliance. In cases where the subject does not return for the rescheduled visit or cannot be reached to reschedule the missed visit, the site should make every effort to regain contact with the subject (3 telephone calls to the subject should be made and if that fails, then a certified letter is sent to the subject's last known mailing address) so that they can be considered withdrawn from the study for disposition purposes. These contact attempts should be documented in the subject's medical record. Should the subject continue to be unreachable, then and only then will she be considered to have withdrawn from the study with a primary reason of "Lost to Follow-up". For all other subjects withdrawing from the study, an alternative reason for discontinuation should be recorded in the eCRF.

If a subject elects to discontinue treatment/EP she should be encouraged to stay in the study and complete all follow-up visits and procedures and have all scheduled immune assessment blood samples collected as indicated in the Schedule of Events ([Table 1](#)). At a minimum, the Investigator should make every effort to have the subject complete all assessments designated for the discharge visit, Week 100 for subjects completing the study prior to Amendment 5.0.

For subjects completing the study under Amendment 5.0, the discharge visit will be Week 78 unless the subject was beyond Week 78, then the discharge visit will be the next scheduled visit per the schedule of events. The updated consent for Amendment 5.0 must be obtained before final visit procedures are performed. For subjects completing the study at Week 78, the repeat cervical colposcopy will be performed at Week 74 or the discharge visit. The socio-behaviorial assessment scheduled for Week 100 will be done at the final discharge visit for subjects completing the study before Week 100. A subject will be considered to have completed the study when all scheduled study treatments and follow-up visits are completed.

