#### 1.1.4 RECURRENT DISEASE WITH CURRENT THERAPEUTIC OPTIONS

There remains an unmet medical need with regard to effective treatment options for vulvar HSIL. Current treatment options show a significant risk of vulvar HSIL recurrence, often requiring multiple, repeat treatments. Progression to vulvar cancer following current vulvar HSIL treatments can also occur within 1 year of treatment and for up to 20 years post treatment. The current treatment options for vulvar HSIL are surgical excision, laser ablation, and off-label medical therapy. The rate of HPV-associated vulvar HSIL recurrence after surgical treatment is high; post-treatment recurrence rates are as high as 45% at three years post-treatment with all currently available treatment regimens [14, 15].

Wide local excision is the 'preferred initial intervention' by ACOG if invasive carcinoma is suspected, and, vulvar biopsy shows vulvar HSIL. If occult invasive disease is not suspected, vulvar HSIL treatment includes surgery: wide local excision, partial vulvectomy, skinning vulvectomy, or simple vulvectomy, laser ablation. Surgical treatments are associated with disruption of normal anatomy and subsequent issues with body image and sexual dysfunction. Medical therapies have been investigated as a means to avoid these negative outcomes. Clinical trials have shown the application of topical imiquimod to be effective however it has not been approved by the U.S. Food and Drug Administration for this indication. Inconsistent treatment efficacy results have been shown with photodynamic therapy, topical cidofovir and topical 5-fluorouracil.

Vulvar HSIL may be followed (with interim observation, but, no intervention) if the patient is young, and, or, if the immune-compromised state is being corrected. Women with pathologic clear margins (no vulvar HSIL) after surgical excision have a lower, yet significant, risk of recurrence compared to women with involved margins. Laser ablation is acceptable treatment for vulvar HSIL when cancer is not suspected, although the risk

of recurrence is slightly higher compared to wide local excision. Laser treatment of vulvar HSIL requires destruction of cells through the entire thickness of the epithelium including hair follicles (in hair-bearing areas of the vulva). In areas without hair, ablation should extend through the dermis. Post-treatment recurrence rates exceed 30% (for all treatment regimens), and is higher with positive excision margins [16].

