### 2.1 PRIMARY OBJECTIVE AND ENDPOINT

Objective	Endpoint
Determine the efficacy of four doses of VGX-3100, alone or in combination with imiquimod, with respect to combined histopathologic regression of vulvar HSIL and virologic clearance of HPV-16/18 in vulvar tissue	Proportion of subjects with no histologic evidence of vulvar HSIL  and no evidence of HPV-16/18 at Week 48 in vulvar tissue samples (i.e. collected via biopsy or excisional treatment)  .

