### 3.2.1 DEFINITION OF RESPONDER AND NON-RESPONDER FOR THE PRIMARY ENDPOINT

A treatment responder is defined as a subject with no histologic evidence of vulvar HSIL and no evidence of HPV-16 or HPV-18 in vulvar tissue at evaluation and who did not receive any non-study related treatment for vulvar HSIL. A treatment non-responder is a subject with histologic evidence of vulvar HSIL or vulvar carcinoma at evaluation, or a subject with evidence of HPV-16/18 at evaluation, or a subject who received non-study related treatment for vulvar HSIL. Any case of histologically confirmed progression to carcinoma according to the PAC is considered a non-responder.

Responder and non-responder definitions ([Table 3](#)) take into account both histopathologic regression of vulvar HSIL and virologic (HPV-16/18) clearance from tissue samples since HPV persistence is an important factor in the clinical progression of HSIL.

Table 3: Definition of Responder and Non-responder for the Primary Endpoint	
Responder	Non-Responder
Subject with no histologic evidence of vulvar HSIL AND Subject with no evidence of HPV-16 or HPV-18 in vulvar tissue at evaluation AND Subject who did not receive any non-study related treatment for vulvar HSIL	Subject with histologic evidence of vulvar HSIL or vulvar carcinoma at evaluation OR Subject with evidence of HPV-16 or HPV-18 in vulvar tissue at evaluation OR Subject who received non-study related treatment for vulvar HSIL

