## **4. SELECTION OF SUBJECTS**

### **4.1 INCLUSION CRITERIA**

Each subject must meet all of the following criteria to be enrolled in the study:

1. Must understand, agree and be able to comply with the requirements of the protocol. Subjects must be willing and able to provide voluntary consent to participate and sign a Consent Form prior to study-related activities;
2. Women aged 18 and above;
3. Vulvar infection with HPV types 16 and/or 18 confirmed by screening biopsy;
4. Vulvar tissue specimen/blocks must be collected within 10 weeks prior to anticipated date of first dose of study drug and have confirmed histologically confirmed vulvar HSIL by the Pathology Adjudication Committee at screening;

5. Must be judged by the Investigator to be an appropriate candidate for the protocol-specified procedure (i.e. excision or biopsy) required at Week 48;
6. Must have vulvar HSIL that is accessible for sampling by biopsy instrument and of adequate size to ensure that a visible lesion remains after an approximately 4 mm screening biopsy;
7. Must have vulvar HSIL that can be completely demarcated for area measurement;
8. Must meet one of the following criteria with respect to their reproductive capacity:
  - a. Is post-menopausal as defined by spontaneous amenorrhea for more than 12 months or spontaneous amenorrhea for 6-12 months with FSH level >40 mIU/mL;
  - b. Is surgically sterile due to absence of ovaries or due to a bilateral tubal ligation/occlusion performed more than 3 months prior to screening;
  - c. Women of Child Bearing Potential (WOCBP) are willing to use a contraceptive method with failure rate of less than 1% per year when used consistently and correctly from screening until 6 months following the last dose of investigational product. Acceptable methods are the following:
    - i. Hormonal contraception: either combined or progestin-alone including oral contraceptives, injectable, implants, vaginal ring, or percutaneous patches. Hormonal contraceptives must not be used in subjects with a history of hypercoagulability (e.g., deep vein thrombosis, pulmonary embolism);
    - ii. Abstinence from penile-vaginal intercourse when this is the subject's preferred and usual lifestyle;
    - iii. Intrauterine device or intrauterine system;
    - iv. Male partner sterilization at least 6 months prior to the female subject's entry into the study, and this male is the sole partner for that subject.

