#### **7.1.4 EVENT REPORTING FOR DISEASE PROGRESSION OR EXCLUSIONARY HISTOLOGIC FINDINGS POST-STUDY TREATMENT**

After starting study treatment, if there is histologic confirmation of progression of HSIL to microinvasive or invasive squamous cell carcinoma, the event must be reported as an SAE. For the finding of carcinoma, subjects should be managed per routine standard of care (i.e. surgical excision), discontinued from study treatment but continue on study without further biopsy. Post-study treatment histologic diagnosis of carcinoma should also be reported as an SAE. In both instances the condition for SAE reporting should be categorized as a medically important event unless another criterion is met.

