## 8. STATISTICAL ANALYSIS PLAN

### 8.1 GENERAL CONSIDERATIONS

The statistical analysis of the data will be performed by Inovio Pharmaceuticals or its representative.

This is a two-arm, multi-center, open-label randomized clinical trial of VGX-3100 and VGX-3100 with imiquimod, in subjects with a histologic diagnosis vulvar HSIL and confirmed vulvar infection with HPV types 16 and/or 18. The study's primary endpoint is binary: regression of vulvar HSIL and viral clearance of HPV-16 and/or HPV-18 from vulvar tissue based on tissue collected at Week 48. The primary hypothesis is that each of the treatment arms will result in regression of HSIL and clearance. Secondary efficacy analyses pertain to regression, clearance of HPV-16 and/or HPV-18 infection, regression to normal, non-progression, and anatomic extent. Other secondary analyses concern safety and cellular immunological measures. Exploratory efficacy analyses concern extended dosing with respect to regression, clearance, and anatomic extent, and clearance outside of the vulva. Other exploratory analyses pertain to humoral, cellular, and tissue immunological measures and patient-reported outcomes.

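### Section 4.3.2 stops biopsies for any woman who becomes ineligible, and does not keep the Week 48 biopsy for one who loses only dosing eligibility and has had no non-study HSIL treatment

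*Protocol*

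**What the plan says.** All references are to Protocol Version 5.0.

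- **The rule.** Section 4.3.2 applies to "Subjects who become ineligible to continue on study based on no longer meeting exclusion criteria". These women "should be discontinued from study treatment, managed per routine standard of care and should continue on study without further biopsy". No visit is exempted and no medical reason is required.
- **The neighbouring text.** The same section wants every woman who starts treatment to be encouraged through all phases, including those who stop treatment. A woman who chooses to stop dosing is to be encouraged to complete all follow-up visits and procedures.
- **The endpoint.** Section 2.1 requires "no evidence of HPV-16/18 at Week 48 in vulvar tissue samples", together with no histologic HSIL. Section 8.1 repeats that the endpoint covers "viral clearance of HPV-16 and/or HPV-18 from vulvar tissue based on tissue collected at Week 48". Section 4.1 makes it an entry condition that each woman be an "appropriate candidate for the protocol-specified procedure (i.e. excision or biopsy) required at Week 48".
- **Outcome without Week 48 tissue.** Under Section 3.2.1 and Table 3, "a subject who received non-study related treatment for vulvar HSIL" is a non-responder. So is any woman with histologically confirmed progression to carcinoma.
- **Analysis.** Section 8.4 limits mITT, the primary efficacy set, to dosed women who have the endpoint in question. Section 8.13 rules out imputation.

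**The concern.** Elsewhere in the protocol, the instruction to continue without biopsy goes to women whose outcome is settled or about to be. In Section 3.2 they are women sent to surgical or standard treatment after the Week 48 result, or to surgery for worsening disease. In Section 7.1.4 they are women with carcinoma. Section 4.3.2 attaches the same instruction to loss of eligibility alone, when the outcome may still be unknown.

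Whether a woman off dosing is biopsied at Week 48 would then depend on why she stopped: yes if she chose to stop, no if she became ineligible. The rule itself would create the missing outcome, and the loss may be related to prognosis. A separate analysis plan could add a sensitivity analysis, but it could not supply tissue that was never taken.

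**Working it through.** **Step 1. Who has a primary outcome once biopsies stop before Week 48?**

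| Woman | Primary outcome |
|---|---|
| Carcinoma found | Non-responder (Section 3.2.1) |
| Non-study HSIL treatment given | Non-responder (Table 3) |
| Neither, no tissue taken | None: out of mITT (8.4), not imputed (8.13) |

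Only the third row is affected.

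**Step 2. Does another provision rescue the third row?** Section 8.9 opens the efficacy window 14 days before the visit week and sets no end, so later tissue might count. But Section 4.3.2 bars the later biopsies too. Section 6.13 lets medical judgement override the schedule when progression is suspected. That is a safety biopsy and does not replace the scheduled outcome biopsy. Swabs do not count, because the endpoint needs tissue.

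**Step 3. Can the third row contain anyone?** Immunosuppression is exclusion 13 in Section 4.2, and Section 6.15 bars disease-modifying immunosuppressive drugs throughout the study, so this condition can arise after entry. Routine care need not mean HSIL treatment: Section 1.1.4 says that vulvar HSIL "may be followed (with interim observation, but, no intervention) if the patient is young, and, or, if the immune-compromised state is being corrected". That is background on general practice, not an instruction to sites, so it shows only that the case is possible.

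**Step 4. Reproduce the stated sample size.** Inputs from Section 8.3: 36 women randomised 2:1 (24 and 12), null rate 2%, assumed rates 20% and 28%, one-sided 0.025, 90% evaluable. The critical count is the smallest r with P(X ≥ r | n, 0.02) < 0.025, and power is P(X ≥ r | n, p).

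- The smallest evaluable numbers from which power stays at or above 80% are 21 (r = 3, 82.1%) and 10 (r = 2, 81.7%).
- 21/0.9 = 23.3, rounded up to 24. 10/0.9 = 11.1, rounded up to 12. Total 36, as stated.

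**Step 5. Lose one woman.** The plan expects 0.9 × 24 = 21.6 and 0.9 × 12 = 10.8 evaluable, or 22 and 11 to the nearest woman. Enrolment to the combination arm was later halted, so its figures describe the plan as first sized.

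| Arm | n | r | Power |
|---|---|---|---|
| VGX-3100 alone (20%) | 22 | 3 | 84.6% |
| | 21 | 3 | 82.1% |
| With imiquimod (28%) | 11 | 2 | 85.8% |
| | 10 | 2 | 81.7% |

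If the expected numbers are rounded down to 21 and 10 instead, one further loss gives 79.4% (n = 20) and 76.6% (n = 9). That assumes a loss beyond the 10% already allowed, and the documents do not say there would be one.

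**Step 6. Effect on the result.** The critical counts do not change, so dropping one non-responder only moves the estimate: 4/22 = 18.2% to 4/21 = 19.0%, or 3/11 = 27.3% to 3/10 = 30.0%. As an illustration in the other direction, suppose the unbiopsied woman would have responded and the arm sits at the margin. Then 3/22 (Clopper-Pearson lower 95% bound 2.9%, p = 0.0093) passes the 2% threshold, and 2/21 (lower bound 1.2%, p = 0.065) fails it.

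**The case against.** The best reply is that Section 4.3.2 echoes Section 7.1.4, where women with carcinoma are to be "managed per routine standard of care (i.e. surgical excision") and then followed without biopsy. On that reading the clause covers only women whose outcome is known, and excised tissue goes to the pathology committee and counts for the endpoint. The likeness is real and is a good reason to expect a small group. But Section 4.3.2 refers to the exclusion criteria in general and does not mention carcinoma, so its text does not carry that limit.

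Several further points stand:

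- The trigger is garbled. Taken literally, no longer meeting exclusion criteria describes no correctly enrolled woman. The point rests on the evident intent, that she has come to meet one.
- Some routes into the group are weak. Exclusions 15 and 16 concern vaccines near a dose, the last dose before Week 48 is at Week 24, and nothing says a mistimed vaccine ends eligibility. Pregnancy has its own rule in Section 7.1.11, and Section 6.3.4.7 requires a negative test before biopsy. A bleeding disorder or blood thinners (exclusion 18c) might themselves contraindicate the biopsy.
- The verb is "should" in effect, advice rather than prohibition, and biopsy for suspected progression survives.
- Sparing a woman a research biopsy once she is off treatment is a defensible wish. However, this biopsy was already scheduled, and she may decline it.

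A reader might infer that every woman who becomes ineligible loses her primary outcome. The documents do not support that: those with carcinoma or non-study HSIL treatment stay in the analysis as non-responders.

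**Conclusion.** The point holds in a narrow form. As written, and with the trigger read as intended, Section 4.3.2 removes the primary outcome of a woman who loses only dosing eligibility before Week 48 and has had no non-study HSIL treatment. New immunosuppression is the clearest example. This conflicts with the section's own aim for women who stop treatment.

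The size is unknown and probably small. A reader might infer that the trial falls below its stated 80% power or that its conclusion is at risk. Neither is shown: no frequency is given, the 90% evaluable assumption absorbs some loss, and one woman fewer from 22 and 11 leaves power above 80%. The change from 3/22 to 2/21 needs an unbiopsied responder exactly at the margin. That the loss is informative is a possibility, not a finding. This is a cheap improvement that avoids a missing outcome, not a flaw in the design as a whole.

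**What to change.** Make two changes to Section 4.3.2.

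1. Reword the trigger to cover women who come to meet an exclusion criterion after enrolment.
2. State that loss of dosing eligibility alone does not cancel the scheduled Week 48 visit and biopsy, unless (a) the biopsy is medically contraindicated, including in pregnancy under Section 7.1.11, (b) carcinoma has been found, or (c) the woman has already received non-study HSIL treatment and counts as a non-responder under Table 3.

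The cost is a sentence or two of protocol text, with nothing added to the schedule of events. The downside is that a few women off study treatment keep one punch biopsy that was already scheduled, which they may decline.

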### 4.3.3 SPONSOR NOTIFICATION OF DISCONTINUATION/WITHDRAWAL

The Investigator or study coordinator must notify the Sponsor immediately when a subject has been discontinued/withdrawn due to an AE. If a subject discontinues from the study or is withdrawn from the study prior to study completion, all applicable activities scheduled for the final study visit should be performed at the time of discontinuation. The Investigator will make every effort to have all scheduled immune assessment blood samples collected as indicated in the Schedule of Events in the synopsis, [Table 1](#). Any AEs and/or SAEs present at the time of discontinuation/withdrawal should be followed in accordance with the safety requirements outlined in [section 7.1](#).

### 4.3.4 REASON FOR DISCONTINUATION/WITHDRAWAL

The primary reason for a subject discontinuing further dosing or withdrawal from the study itself is to be selected from the following standard categories and recorded on the eCRF:

- Adverse event (adverse reaction): Clinical or laboratory events occurred that, in the medical judgment of the Investigator for the best interest of the subject, are grounds for discontinuation. This includes serious and non-serious AEs regardless of relation to study drug.
- Death
- Subject voluntarily withdrew consent: The subject desired to withdraw from further participation in the study in the absence of an Investigator-determined medical need to withdraw. If the subject gave a reason for withdrawal, it must be recorded on the eCRF. This reason does not allow for further data collection and should not be selected if follow-up data collection of this subject is anticipated by the subject.
- Investigator decision to withdraw the subject from participation: Investigator determined a maternal obstetrical or medical need to withdraw the subject. Investigator must consult the medical monitor before withdrawing a subject from participation in the study.
- Protocol violation: The subject's findings or conduct failed to meet the protocol entry criteria or failed to adhere to the protocol requirements (e.g., treatment noncompliance, failure to return for defined number of visits). The violation should be discussed with the Sponsor's Medical Monitor prior to discontinuation of study treatments or study withdrawal.
- Lost to follow-up: The subject fails to attend study visits and study personnel are unable to contact the subject after at least 3 repeated attempts including letter sent by certified mail or equivalent.

